## SUMMARY

**Importance:** After a primary total knee arthroplasty (TKA), we anticipate that obese individuals are more likely to experience a of periprosthetic joint infection (PJI). Knowing the microbial profile in obese patients can potentially help in choosing the proper prophylactic measures for this group as well as tailoring the empirical antibiotics in relation to PJI in obese patients.

**Objective:** To compare incidence of PJI revisions within 2 years after TKA in obese vs non-obese OA patients. Secondarily: To compare microbial profiles of infections in these groups in two time windows: early ( $\leq 90$  days) vs late (91–730 days) and incidence of revisions due to all causes within 2 years. **Design and Setting:** We will include patients having primary knee arthroplasty using Danish national registers. Patients will be stratified into anthropometric groups, referred to as exposed and unexposed to obesity, based on their baseline Body Mass Index (BMI). Participants included in the analysis population will be followed up for 2 years, until first revision, death or migration whichever comes first.

**Participants:** We will include adult patients with available weight and height data with primary/idiopathic or secondary (due to meniscus or cruciate ligament lesion) OA who received primary TKA in the period from 2011-01-01 and 2021-02-28. Patients will be identified from the Danish knee arthroplasty register.

**Exposure and Comparator:** The cohort will be divided into obese (exposed), defined as body mass index (BMI)  $\geq 30$  kg/m $^2$ ; and non-obese (unexposed), defined as BMI  $< 30$  kg/m $^2$ .

**Main Outcomes and Measures:** The primary outcome will be revision due to prosthetic joint infection (PJI) within 730 days following TKA. Secondary endpoints will then be to examine revision due to all causes within 730 days following TKA and type of microbial infection between obese and non-obese in the first 90 days and the period from 91 days to 730 days following TKA.

**Planned Statistical Analyses:** We will use descriptive statistics to summarize the baseline characteristics of the two groups. Hazard ratios with corresponding two-sided 95% confidence intervals (95%CIs) for experiencing the outcome will be estimated using a Cox proportional hazards regression model. We will fit both unadjusted (crude) model and a propensity score adjusted model calculated based on age, sex, highest completed education, household income, comedication, and Elixhauser Comorbidity Measure (ECM), all collected up to the day of surgery. Stratified analyses will categorize PJI cases by bacterial infection and compare crude proportions between groups based on the absolute risk difference with 95% confidence intervals.

**Ethical Considerations and Registration:** The study and its statistical analysis plan will be registered in clinicaltrials.org prior to conducting the study.

## INTRODUCTION

Knee arthroplasty are effective treatments of end-stage joint disease not responding to other treatment measures. Periprosthetic Joint infection (PJI) is an unusual but devastating complication of joint arthroplasty. It carries significant burden on patients' morbidity in terms of severe pain, decreased physical activity and quality of life and may lead to death. The microbial profile of PJI significantly influences treatment outcomes, with Gram-negative bacteria (GNB), including multidrug-resistant (MDR) pathogens having highest rate of failures. coagulase negative staphylococcus was also found to experience a high risk of re-revision. Studies have linked increasing body mass index (BMI), smoking, male gender, diabetes, rheumatoid arthritis, depression, history of steroid use and previous joint surgery with an increased risk of PJI after Total Knee Arthroplasty (TKA); from these, increasing BMI is found to be the most consistent risk factor for developing PJI.

Theories to understand and by that prevent PJI in overweight and obese patients have been proposed; under-dosed prophylactic antibiotics, increased surface tension, increased blood glucose and increased bacterial colonization of the skin in the groin are possible explanations of the association between PJI and overweight. A previous study showed that obese patients have higher rates of polymicrobial and Gram-negative early periprosthetic joint infections of the hip than non-obese patients. This study looked however only in early infections treated with debridement, antibiotics and implant retention (DAIR). A single previous cohort study from England and Wales found that the mean BMI was higher in Mixed genus PJI. We anticipate that knowing the microbial profile in obese patients can help in choosing the proper prophylactic measures for this group as well as tailoring the empirical antibiotics in relation to PJI in obese patients.

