## Data sources

The Danish Civil Registration System (DCRS) contains information on the CPR number, vital and migrant status, cohabiting status, and municipality of residence. The Danish Knee Arthroplasty Register (DKR) is nation-wide register that contains information on all primary knee arthroplasty procedures and revisions performed in Denmark, e.g., baseline characteristics as age, sex, BMI, at the time of TKA operation. The registry started in 1997 and the reporting to the registry became mandatory since 2006. DKR is known for high degree of coverage and completeness. The Danish Microbiology Database (MiBa) is a national database containing data from all samples received by the Danish clinical microbiology departments from both hospitals and general practices with complete coverage since 2010.

The Danish National Patient Register (DNPR) is a valuable tool for epidemiological research, providing longitudinal registration of diagnoses, treatments, and examinations derived from every hospital contact in Denmark with complete nationwide coverage since 1978. The Danish National Prescription Registry has kept information on all prescriptions for drugs dispensed by community pharmacies in Denmark since 1994 according to Anatomical Therapeutic Chemical (ATC) classification system (ATC codes). Data from the Danish National Prescription Registry does not include hospital dispensaries.

The Danish Registers on Personal Income and Transfer Payments contains more than 160 variables including salaries, entrepreneurial income, taxes, public transfer payments, capital income, private pension contributions, and pay-outs. In addition, Statistics Denmark provide more detailed registers on specific income transfers, including sickness benefit, old age pension, disability pension, and cash and unemployment benefits. The Danish Population Education Register provides information on education status on Danish population, and it carries high degree of validity and coverage.

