## Covariates

The cohort will be divided into two groups at baseline: obese, defined as  $\text{BMI} \geq 30 \text{ kg/m}^2$ , and non-obese, defined as  $\text{BMI} < 30 \text{ kg/m}^2$ . For descriptive purposes and adjusting, we will be using the following pre-TKA exposure covariates: age (years) at the time of TKA, sex (coded as female=1; male = 0), household income (at the year before KA, categorized into quartiles), highest completed education (at the year of KA, categorized into 3 categories: <11, 11 to 15, and >15 years). Comedication (at least one redeemed prescription 365 days earlier to index KA - 60 days for antibiotics): 1) Glucose-lowering due to the association between DM and surgical complications. 2) Antithrombotic medications and 3) NSAIDs because of the possible postoperative bleeding-related complications and 4) Antiresorptives due to the possible increased risk of revision. The last covariate to be included in matching and adjustment is Elixhauser Comorbidity Measure (ECM) (at the year of KA, categorized into 3: 0, 1-2 and  $\geq 3$ ), ECM is validated comorbidity scoring measure that has shown highest discriminative ability for the occurrence of all categories of postoperative adverse outcomes following orthopedic surgeries.

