## Statistical Methods

We will use descriptive statistics to summarize baseline characteristics of the two groups and will compare them using standardized differences. The 2-year (730 days) cumulative incidence of PJI will be reported for both groups. Hazard ratios with corresponding two-sided 95% confidence intervals (CIs) will be estimated using a Cox proportional hazards regression model. We will fit both unadjusted (crude) models and propensity adjusted models using inverse probability of treatment weighting (IPTW). For the adjusted model, propensity scores will be calculated based on age in years, female sex, completed education, household income, comedications, and ECM (all collected prior to surgery). Subsequent stratified analyses will categorize the observed PJI cases by bacterial infection type (within the first 90 days postoperatively or between 91 days and 2 years) and compare crude proportions between groups based on the absolute risk difference with 95% confidence intervals.

[figure not shown]
We present several analyses corresponding to the main results with 95% confidence intervals rather than P values, and comply with 2 Acta Orthopaedica principles for concluding whether scientifically important differences exist:

- A statistically non-significant test is not sufficient to claim "no difference." To show "no difference," a smallest clinically relevant size of the difference (it might be 0) must be defined. If all clinically relevant differences are excluded from the difference's confidence interval, a "no difference" or similarity/comparability conclusion is reasonable.
- A statistically significant test does not necessarily imply a clinically important difference. The importance of the tested null hypothesis depends on the smallest clinically relevant difference that should be defined a priori. If the difference's confidence interval excludes all clinically irrelevant differences, a conclusion concerning the existence of a clinically important difference is reasonable.

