| BMI, kg/m                      |       |           |           |
| Highest completed Education:               |       |           |           |
| <11 years, no. (%)                         |       |           |           |
| 11 to 15 years, no. (%)                    |       |           |           |
| >15 years, no. (%)                         |       |           |           |
| Household income:                          |       |           |           |
| Lowest (1 st quantile), no. (%) |       |           |           |
| Low (2 nd quantile), no. (%)    |       |           |           |
| Medium (3 rd quantile), no. (%) |       |           |           |
| High (4 th quantile), no. (%)   |       |           |           |
| Comedications:                             |       |           |           |
| Antithrombotics, no. (%)                   |       |           |           |
| Antibiotics, no. (%)                       |       |           |           |
| Glucose-Lowering, no. (%)                  |       |           |           |
| NSAIDs, no. (%)                            |       |           |           |
| Antiresorptives, no. (%)                   |       |           |           |
| ECM  |       |           |           |
| 0, no. (%)                                 |       |           |           |
| 1 to 2, no. (%)                            |       |           |           |
| ≥ 3, no. (%)                               |       |           |           |

Abbreviations: BMI: body mass index; NSAIDs: Non-Steroidal anti-inflammatory drugs; ECM: Elixhauser Comorbidity measure; Std. Diff: Standardized Difference.

**Figure 2 (Mockup):** Simulated data illustrating the cumulative incidence of A) Prosthetic joint infection (PJI); B) all-cause revision.

**Table 2 (Mockup):** Incidence for Periprosthetic joint infection (PJI) and all cause revision at 2 years in obese and non-obese patients with an unadjusted and adjusted analyses of the Hazard Ratios (HR) between the 2 groups over the full 2-year period

|                             | Obese   | Non-Obese | HR [95% CI*]  |
|-----------------------------|---------|-----------|---------------|
| Crude analyses:      |         |           |               |
| N                           | xx      | xx        |               |
| PJI, no. (%)                | xx (xx) | xx (xx)   | xx [xx to xx] |

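### Steroid use and previous joint surgery are named as PJI risk factors and are at least partly available in the registers, but are absent from the propensity score without a reason

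*Combined protocol and SAP*

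**What the plan says.** The Introduction reports that studies have linked, besides BMI, "smoking, male gender, diabetes, rheumatoid arthritis, depression, history of steroid use and previous joint surgery with an increased risk of PJI".

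Statistical Methods defines the adjusted model by inverse probability weighting: "propensity scores will be calculated based on age in years, female sex, completed education, household income, comedications, and ECM (all collected prior to surgery"). The Summary gives the same list.

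The Covariates section opens with "For descriptive purposes and adjusting, we will be using the following pre-TKA exposure covariates". Its drug definition reads "Comedication (at least one redeemed prescription 365 days earlier to index KA - 60 days for antibiotics"). The numbered drug classes are glucose-lowering drugs, antithrombotics and NSAIDs, ending with "4) Antiresorptives due to the possible increased risk of revision". The Elixhauser measure enters in three levels: 0, 1-2, and 3 or more.

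The Table 1 mock-up has five rows under its comedication heading: the four numbered classes and a row beginning "Antibiotics, no". It has no row for steroids or previous surgery.

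According to Data sources, the Prescription Registry holds "all prescriptions for drugs dispensed by community pharmacies in Denmark since 1994", but not hospital-dispensed drugs. The National Patient Register holds hospital diagnoses and treatments.

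After Table 1's introduction of the groups, the decision rule in Statistical Methods takes a clinically meaningful increase in risk as excluded if the upper 95% limit of the hazard ratio is below 1.5.

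**The concern.** In an observational comparison of BMI groups, the propensity score is the only protection against confounding. When a plan names a risk factor for its primary outcome and lists a register that could measure it, a reader expects to see it in the score or to see why it was left out. For steroid use and previous joint surgery the plan does neither. The reasons given for the four numbered drug classes are diabetes, bleeding and revision risk, so none of them was chosen to cover steroid exposure. Nothing in the documents says that a three-level comorbidity score captures a drug exposure or an earlier operation.

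If either factor differs between obese and non-obese patients after weighting, the adjusted hazard ratio and its confidence limits shift by the same factor. The conclusion depends on one limit compared with 1.5, so even a shift of a few percent could alter it when the limit is close. The rule does not say whether it applies to the crude or the adjusted hazard ratio; I assume the adjusted one.

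**Working it through.** **Step 1: named risk factors against the adjustment set.**

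| Factor named in the Introduction | In the propensity score? | Obtainable, according to Data sources? |
|---|---|---|
| Male gender | Yes | Yes |
| Diabetes | Yes, through glucose-lowering drugs | Yes |
| Rheumatoid arthritis, depression | At most through the Elixhauser level; its components are not listed | Hospital diagnoses |
| Smoking | No | Not described as held in any listed register |
| Steroid use | No | Partly (community prescriptions only) |
| Previous joint surgery | No | Hospital treatments |

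Only the last two are absent and at the same time obtainable at least in part.

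**Step 2: the plan's own figure.** A 2-year incidence of 1% raised by 50% is 1.5%. The matching hazard ratio is ln(1 - 0.015)/ln(1 - 0.01) = 1.504, which agrees with the stated 1.5.

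**Step 3: size of a possible shift.** For one omitted binary factor and a rare outcome, the hazard ratio is multiplied by

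B = [1 + p1(R - 1)] / [1 + p0(R - 1)],

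where p1 and p0 are the factor's prevalence in obese and non-obese patients (as left after weighting) and R is its effect on PJI. The documents give none of these, so all inputs below are assumptions.

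- Steroids, 8% vs 5%, R = 2.0: B = 1.08/1.05 = 1.029.
- Previous surgery, 25% vs 35%, R = 1.5: B = 1.125/1.175 = 0.957.
- Both, if they act independently: 1.029 × 0.957 = 0.985.

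A wider range of assumptions:

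| p1 vs p0 | R = 1.5 | R = 2 | R = 3 |
|---|---|---|---|
| 5% vs 5% | 1.000 | 1.000 | 1.000 |
| 6% vs 4% | 1.010 | 1.019 | 1.037 |
| 10% vs 5% | 1.024 | 1.048 | 1.091 |
| 20% vs 10% | 1.048 | 1.091 | 1.167 |
| 5% vs 10% | 0.976 | 0.955 | 0.917 |

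The shift can be upward, downward or nil.

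**Step 4: effect on the 1.5 rule.** Suppose B multiplies the upper limit and leaves the interval's width on the log scale unchanged.

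- B = 1.029: a limit that would be between 1.5/1.029 = 1.458 and 1.5 without the bias is read as above 1.5.
- B = 0.957: a limit that would be between 1.5 and 1.5/0.957 = 1.567 is read as below 1.5, so the rule is met wrongly. For example, 1.55 × 0.957 = 1.48.
- B = 0.985: the misread zone is only 1.5 to 1.5/0.985 = 1.523.

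**The case against.** **No link with obesity is shown.** A confounder must be related to BMI as well as to PJI, and the Introduction ties these factors to PJI only. This stands: confounding is possible but not demonstrated. It does not remove the case for including the two factors, because a predictor of PJI that proves to be balanced gives B = 1.00.

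**Over-adjustment.** If steroid use or earlier surgery is partly a consequence of long-standing obesity, adjusting for it removes part of the effect under study. The Introduction itself offers raised blood glucose as a possible explanation of the link between overweight and PJI. This stands in part. Using only pre-surgery values keeps out anything that follows the operation but does not settle what came before it. Reporting the estimate with and without the two terms shows the reader how much depends on them. The plan already accepts a similar risk by adjusting for glucose-lowering drugs.

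**The effect is small and may cancel.** True under the two assumed examples, whose net factor is 0.985. Other assumptions give more, and the documents do not say which apply.

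**Steroid capture is incomplete.** Also true, since hospital-dispensed drugs are missing. Partial control, stated as such, is still better than an omission without comment.

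**Antibiotics.** A reader might infer from the numbered list that recent antibiotics are left out of the score. The text does not support that. They sit inside the comedication definition with their own window, in a list introduced as serving adjustment; Table 1 shows them as a comedication; and Statistical Methods puts comedications in the score. The natural reading includes them, and only the numbering is out of step.

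**Conclusion.** The point holds in a limited form. Two PJI risk factors that the plan names, and can measure at least in part, are missing from the propensity score without explanation. The adjusted hazard ratio may therefore carry residual confounding that could be partly avoided. The assumed examples give factors of 1.029 and 0.957, and the wider assumed range runs from 0.917 to 1.167. The documents fix neither the size nor the direction. The 1.5 conclusion is at risk only if the upper limit falls close to that value.

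Three stronger readings are not supported:

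- That the adjusted hazard ratio is shown to be confounded: no association of either factor with obesity is given.
- That type of osteoarthritis (primary or secondary) must also enter the score: no section links it to PJI.
- That adding variables removes bias at no cost: steroid capture is partial and some over-adjustment is possible.

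This is an inexpensive improvement to make before analysis, not a flaw that invalidates the plan.

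**What to change.** In Covariates and Statistical Methods, and in the matching sentence of the Summary:

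1. Add redeemed systemic corticosteroids (at least one prescription in the 365 days before TKA) to the propensity score, and state that hospital-dispensed drugs are not captured.
2. Add previous knee surgery before TKA, from the National Patient Register. Say that this narrows the Introduction's wider category of joint surgery to the knee.
3. Report the adjusted hazard ratio with and without these two terms, and add both as rows in Table 1.
4. Number antibiotics (60-day window) as item 5 of the comedication list so that it matches Table 1. This is a wording correction only.

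If either variable is left out after all, give the reason.

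The cost is two more code lists from registers the plan already describes, one more reported estimate, incomplete steroid capture, and possible slight over-adjustment if either factor is partly a result of obesity.

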## Objectives

The primary objective is to compare the incidence of periprosthetic joint infection (PJI) within 2 years of surgery between obese and non-obese patients undergoing primary total knee arthroplasty (TKA) for knee osteoarthritis. Subsequently examine the microbial profiles associated with PJI in these groups within the first 90 days and in the period from 91 days to 2 years following surgery. Finally we will compare the incidence of revision due to all causes within 2 years of surgery between obese and non-obese patients undergoing primary total knee arthroplasty.

## Study design

The study is designed as a nationwide, register-based study investigating the influence of obesity on the microbial profile of PJI after TKA. The study will follow the REporting of studies Conducted using Observational Routinely-collected Data (RECORD) guidelines. We will be comparing the microbial profile of obese patients with BMI of  $30 \text{ kg/m}^2$  (exposed) with non-obese (unexposed) patients, defined as  $\text{BMI} < 30 \text{ kg/m}^2$ .

## Setting

All Danish residents have a personal identification number consistent throughout all registers making register-linkage possible. We will include patients with PJI diagnosis after their primary hip or knee

arthroplasty using Danish national registers. Patients will be followed up for 2 years, until first revision, death or migration whichever comes first.

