## Study population

In order to be eligible, we will include adult patients with primary or secondary osteoarthritis (due to meniscus or cruciate ligament lesion) who underwent primary TKA between January 1, 2011, and February 28, 2021, and for whom weight and height data are available. Patients will be identified from the DKR. Patients are followed for 2 years, until first revision, death or migration, whichever comes first.

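### The inclusion sentence in Setting requires a PJI diagnosis and admits hips, against the knee-only TKA cohort defined everywhere else in the plan

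*Combined protocol and SAP*

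**What the plan says.** Setting contains an inclusion statement: "We will include patients with PJI diagnosis after their primary hip or knee" arthroplasty. A page break splits the sentence, but its meaning is clear. It makes infection a condition of entry and covers two joints.

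The other sections that define the population differ:

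- Summary, Design and Setting: "We will include patients having primary knee arthroplasty using Danish national registers".
- Study population: adults with osteoarthritis and recorded height and weight "who underwent primary TKA between January 1, 2011, and February 28, 2021". It adds "Patients will be identified from the DKR", which is the knee register. Infection is not required and hips are not mentioned.
- Objectives: "The primary objective is to compare the incidence of periprosthetic joint infection (PJI) within 2 years of surgery between obese and non-obese patients" having a primary TKA.

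Outcomes and endpoints lists revision for PJI within 2 years as the primary outcome. Statistical Methods reports the 2-year cumulative incidence in each group and a Cox hazard ratio with a two-sided 95% confidence interval. It expects an incidence of about 1% and reads an upper confidence limit below 1.5 as showing no clinically meaningful increase in risk.

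Study design describes the work as "investigating the influence of obesity on the microbial profile of PJI after TKA". It does not mention the incidence comparison that Objectives calls primary.

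**The concern.** The Setting sentence stands in the methods and tells the analyst whom to include. Read literally, it conflicts with the rest of the plan twice: it selects on what is elsewhere the outcome, and it brings in hip patients.

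The first conflict matters more. An incidence near 1% exists only if uninfected patients are in the risk set. If entry requires infection, the proportion with an event no longer measures risk after TKA, and the hazard ratio compares only when infected patients had their event. The main hazard is false reassurance: a case-only hazard ratio sits near 1 and may pass the 1.5 rule even when obesity raises the risk by half or more.

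The plan is to be registered before the study is conducted. A registered plan with two incompatible inclusion statements leaves room for dispute about which population was prespecified.

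**Working it through.** **1. The sections side by side**

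| Section | Joint | PJI required for entry? |
|---|---|---|
| Setting | hip or knee | yes |
| Summary | knee | no |
| Study population | knee, from the knee register | no |
| Objectives | knee | no; PJI is what is compared |
| Outcomes and endpoints | knee | no; PJI revision is the outcome |
| Statistical Methods | – | no; incidence of about 1% expected |
| Study design | knee | sets no PJI entry rule |

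Data sources describes a knee arthroplasty register but no hip register. No hip outcome, table or analysis appears.

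**2. The plan's own figures are coherent under the TKA cohort**

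A 50% increase on 1% is 1.5%. The implied hazard ratio is ln(1 − 0.015) / ln(1 − 0.01) = 1.504, which agrees with the stated 1.5. Conversely, a hazard ratio of 1.5 gives an obese-group risk of 1 − 0.99^1.5 = 1.496%, and a risk ratio of 1.496. The primary comparison can be estimated in this population.

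**3. What happens if only cases enter**

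This is a simplified version of the Setting rule: knees only, and every included patient revised for PJI within 730 days. The risk is then 100% in both groups and the risk ratio is 1.00, whatever the true effect.

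A hazard ratio can still be computed. Take a constant daily hazard λ = −ln(0.99)/730 = 0.0000138 in the non-obese and λ × HR in the obese. Event times among cases follow T = −ln(1 − U(1 − e^(−730λ)))/λ, with U uniform on 0 to 1. Because 730λ is only about 0.01, these times are almost uniform over the 730 days in either group. A Cox fit to 20,000 simulated cases per group gave:

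| True HR | Case-only HR |
|---|---|
| 1.5 | 1.005 |
| 2.0 | 1.014 |

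**4. Effect on the 1.5 rule**

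The documents give neither cohort size nor obese share, so these are assumptions: 10,000 to 40,000 TKAs, 35% to 50% obese, 1% risk in the non-obese. For true hazard ratios of 1.0 to 2.0, about 100 to 600 patients would be retained. An approximate standard error of the log hazard ratio is √(1/d₁ + 1/d₀), where d₁ and d₀ are the case counts in the two groups.

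- 10,000 TKAs, 35% obese, true HR 1.5: d₁ = 3,500 × 0.01496 = 52.4 and d₀ = 6,500 × 0.01 = 65. The SE is 0.186, and the upper limit is about 1.005 × e^(1.96 × 0.186) = 1.45.
- 40,000 TKAs, 50% obese, true HR 1.5: d₁ = 299 and d₀ = 200. The SE is 0.091, and the upper limit is about 1.20.

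Across the assumed range the typical upper limit is about 1.20 to 1.45 for true hazard ratios of 1.5 and 2.0. The rule would typically declare no meaningful increase although the true effect is at or above the margin.

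**5. Organism rows in Table 3**

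This ambiguity does not come from Setting. The outcome list speaks of proportions of bacterial groups, and Statistical Methods categorises observed PJI cases and compares crude proportions, which suggests PJI cases as denominator. The same sentence uses an absolute risk difference, and Table 3 has a single N row at the top, which suggests TKAs.

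Let an organism cause the same share s of PJIs in both groups, with 2-year PJI risks of 1.5% and 1.0% (the two time windows are ignored for simplicity). The difference in share is s − s = 0. The difference in risk per TKA is 1.5% × s − 1.0% × s = 0.5 percentage points × s. With s = 10% as an illustrative assumption, that is 0.15% against 0.10%. Over the whole range of s from 0 to 1 it runs from 0 to 0.5 percentage points. The risk per TKA can thus differ for every organism while the microbial profile is identical.

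**The case against.** The strongest reply is that nobody would carry out the Setting sentence. Study population is the dedicated eligibility section and is explicit. The outcome list, the Cox model, the weighting, the cumulative incidence curves, Table 1 and Table 2 all presuppose a TKA cohort. Setting itself goes on to follow patients until first revision, death or migration, much as Study population does. This stands: the intended cohort is recoverable, and the defect is one inconsistent sentence rather than a disputed design.

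Three stronger readings are tempting, and the documents do not support them.

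- A reader might infer that the plan is divided between a case-only study and a cohort, counting Study design on the case-only side. Study design sets no PJI entry rule. It names the microbial-profile aim, a declared secondary outcome, and omits the primary one.
- A reader might infer that under the Setting rule every patient has the primary event. The sentence gives no time limit and does not require revision, and Definitions includes culture-based routes to PJI beside a registered revision. Late or unrevised infections could enter without the primary event.
- A reader might infer that no hazard ratio could be calculated. One could, as shown above, but it would not measure the effect of obesity on infection risk.

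It is also fair to object that the Table 3 denominator would remain unclear after Setting is corrected. That is right, and it is treated here as a separate repair.

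**Conclusion.** The inconsistency is real and should be corrected before registration. Setting makes PJI an entry condition and admits hips, while the rest of the plan describes a knee-only osteoarthritis cohort with PJI revision as the outcome.

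The harm is conditional on the sentence being applied. In that case the 2-year incidence, the hazard ratio and the 1.5 margin become uninterpretable. The case-only hazard ratios of about 1.00 and 1.01 rest on constant hazards, a 1% baseline risk and all cases occurring within 730 days. If infection timing differed between groups, the figure would reflect timing, which is still not risk. The upper limits of 1.20 to 1.45 rest in addition on the assumed cohort sizes and obese shares. None of these figures predicts the study's result under the Study population definition, where the comparison is sound on this point.

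The open denominator in Table 3 is a genuine but separate ambiguity. It bears on the secondary microbial comparison only.

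**What to change.** - **Setting:** replace the inclusion sentence with: *We will include all patients with a primary TKA for osteoarthritis as defined under Study population; PJI is an outcome, not an inclusion criterion.* This also removes the reference to hips.
- **Study design:** name the 2-year incidence comparison as the primary aim and the microbial profile as secondary.
- **Table 3 and Statistical Methods:** state the denominator of the organism rows, and report both the risk per TKA and the share among PJI cases in each window. The risk per TKA alone mixes overall PJI incidence with microbial profile.

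The cost is two sentences and one table note, with the share among PJI cases shown beside the risk. No additional data are needed.
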